5.2 Study Endpoints

Primary Safety Endpoint:

The primary safety endpoints of the study are the number and severity of treatment emergent adverse events (TEAEs) following administration of multiple doses of SC APL-2.

Primary Efficacy Endpoints:

- Change from baseline in LD
- Change from baseline in Haptoglobin
- Change from baseline in Hb

Secondary Endpoints:

- APL-2 plasma concentrations (and PK parameters as appropriate)
- Change from baseline in FACIT Fatigue Scale score
- Change from baseline in reticulocyte count
- Change from baseline in total bilirubin
- Number of RBC transfusions per month
- Change from baseline in Linear Analog Scale Assessment (LASA) for Quality of Life

Exploratory PD markers include:

- Complement (CH50, AP50, and C3) levels
- C3 deposition on RBC cells
- Clonal distribution of PNH RBCs

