12.2.2 Study Endpoints

12.2.2.1 Safety Endpoints

The primary safety endpoints of the study are the number and severity of TEAEs. Safety will also be assessed through vital signs, 12-lead ECG and laboratory safety data. Changes from baseline will be calculated using the last measurement prior to the start of dosing as baseline.

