12.2.3.1 Adverse Events

Treatment emergent adverse events (TEAE) are defined as those AEs that develop or worsen after the first dose of study medication and up to 30 days beyond the last dose of study medication. The current version of Medical Dictionary for Regulatory Activities (MedDRA) will be used to classify all AEs.

TEAE will be summarized by system organ class and preferred term. Tabulations will be produced for all TEAEs, for those considered potentially treatment related (causality to study drug is reported as possibly or probably, or where causality is not reported) and for TEAE of special interest. Number of subjects reporting SAEs will also be tabulated.

A by-subject TEAE data listing, including verbatim term, preferred term, treatment, severity, and investigator judgment of relationship to treatment, will be provided.

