#### 2.3.1 Primary Endpoints

- Change from baseline in lactase dehydrogenase (LDH)
- Change from baseline in haptoglobin
- Change from baseline in hemoglobin.

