### 2.3.3 Safety Endpoints

- Incidence and severity of treatment-emergent adverse events (TEAEs)
- Changes from baseline in vital signs
- Changes from baseline in laboratory parameters
- Changes from baseline in ECG parameters.

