### 7.1 Adverse Events

AEs will be coded using MedDRA Version 21.0.

An AE (classified by preferred term) that occurs during the treatment phase will be considered a treatment-emergent AE (TEAE) if it has a start date on or after the first dose of investigational product or if it has a start date before the date of the first dose of investigational product, but increases in severity on or after the date of the first dose of investigational product. If more than one AE with the same preferred term is reported before the date of the first dose of investigational product, then the AE with the greatest severity will be used as the benchmark for comparison to the AEs occurring during the treatment phase under the preferred term. An AE that occurs more than 30 days after the date of the last dose of investigational product will not be counted as a TEAE.

An overall summary of the number of subjects with TEAEs will be presented, including the number and percentage of subjects with any TEAEs, serious TEAEs, TEAEs related to investigational product and TEAEs leading to discontinuation of investigational product.

The number and percentage of subjects reporting TEAEs will be tabulated by system organ class (SOC) and preferred term. TEAEs considered related to investigational product will also be summarized by SOC and preferred term. If more than one AE occurs with the same

preferred term for the same subject, then the subject will be counted only once for that preferred term using the most related occurrence for the summarization by relationship to investigational product.

Summary tables will be presented over the whole study and by study part. AEs will be categorized by the Part in which the AE started i.e. an AE which began during Part 1 will be categorized under Part 1 even if it continues into Part 2A (unless it increases in severity during Part 2A, when it will be counted in both Parts 1 and 2A). Summaries will be ordered by descending order of total events.

All TEAEs will be listed by subject and start date. Separate listings of serious TEAEs and TEAEs leading to discontinuation of study drug will also be generated. The listing will also include duration of AE, the part of the study the AE started and the part of the study the AE stopped.

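### The SAP reports the protocol's primary safety endpoint (how many TEAEs, and how severe) as subject counts with no severity table, and does not declare the change

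*SAP*

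**What the plan says.** Protocol 5.2: "The primary safety endpoints of the study are the number and severity of treatment emergent adverse events (TEAEs"). Protocol 12.2.2.1 repeats this: "The primary safety endpoints of the study are the number and severity of TEAEs". The protocol's analysis text in 12.2.3.1 leaves the unit of tabulation open: "TEAE will be summarized by system organ class and preferred term".

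The SAP differs in four places.

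- **2.3.1 Primary Endpoints** holds three laboratory items only. It starts with "Change from baseline in lactase dehydrogenase (LDH") and continues with haptoglobin and hemoglobin. There is no TEAE item.
- **2.3.3 Safety Endpoints** has "Incidence and severity of treatment-emergent adverse events (TEAEs"), without the primary label.
- **7.1 Adverse Events** defines the overall summary in subjects, and then: "The number and percentage of subjects reporting TEAEs will be tabulated by system organ class (SOC) and preferred term". On row order it says: "Summaries will be ordered by descending order of total events". It also says: "All TEAEs will be listed by subject and start date". It specifies no table by severity.
- **15 Changes to Analysis** says only that a subset of the protocol's analyses is needed because enrollment closed at 4 subjects.

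**The concern.** The protocol's endpoint is a count of events together with their severity. The SAP's tables, as specified, answer a different question: how many subjects had at least one event. That loses information at any event rate. Under daily infusion for up to 364 days, infections and injection-site reactions can recur, and Protocol 11.5 lists both as adverse events of special interest. Recurrence is what a subject count cannot show.

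The severity half has a parallel gap. SAP 13.5.5 sets a rule for imputing missing severity for use in incidence summaries, but SAP 7.1 specifies no summary that would use it. So neither half of the protocol's primary safety endpoint has a specified table.

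The protocol means these data to be pooled with Cohort 2 of study APL2-CP-PNH-204 and to support Phase III. The measure should therefore be defined once and declared.

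**Working it through.** The documents give no TEAE rate, so there is no plan figure to reproduce. The main check sets the texts side by side.

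**1. Endpoint against output**

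| Element | Protocol 5.2, 12.2.2.1 | SAP |
|---|---|---|
| Status | Primary safety | Safety, no primary label (2.3.3) |
| Quantity | Number of TEAEs | Incidence (2.3.3); n and % of subjects (7.1) |
| Severity | Part of the endpoint | Named in 2.3.3; no table in 7.1 |
| Change declared | – | Not named in SAP 15 |

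**2. What a row shows.** Suppose subject A has 1 event of a preferred term and subject B has 20. Each adds 1 to the subject count, so the row reads 2 of 4 (50%). The event count is 1 + 20 = 21. The sort key needs that figure, but the SAP does not ask for it to be shown.

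**3. Whether the listing gives one answer.** Protocol 11.3.1 records a change in severity over several days as a new AE. SAP 7.1 counts an event that worsens in a later part in both parts. Take, as an illustration, one reaction that starts in Part 1 at Grade 1 and worsens to Grade 2 in Part 2A:

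- records under Protocol 11.3.1: 2
- count by part under SAP 7.1: 1 in Part 1 + 1 in Part 2A = 2
- episodes: 1

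Neither document says whether the whole-study total is 1 or 2. The sort order by total events has the same ambiguity.

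**4. How far the any-TEAE row could lose resolution.** Inputs: dosing for up to 364 days (Protocol 8.3.2) plus a 30-day TEAE window (SAP 7.1), so 394 days, or 394/365.25 = 1.079 years. With an assumed constant rate r per subject-year, P(at least one) = 1 − exp(−1.079 r), and expected events in 4 subjects = 4 × 1.079 × r.

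| Assumed r per year | P(at least one), 394 days | Expected events, 4 subjects |
|---|---|---|
| 1 | 66% | 4.3 |
| 2 | 88% | 8.6 |
| 4 | 99% | 17.3 |
| 8 | 100% | 34.5 |

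The probability reaches 95% at r = ln(20)/1.079 = 2.78 per year. If rates vary between subjects (gamma-Poisson, shape 1), P = 1 − 1/(1 + 1.079 r), which gives 52%, 68%, 81% and 90% for the same four rates.

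**5. Other rows and parts.** A preferred term at an assumed 0.25 per year gives 1 − exp(−0.25 × 1.079) = 24%. By part, assumed total rates of 0.25 and 2 per month (30.4 days) give:

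- Part 1 (28 days): 1 − exp(−0.25 × 28/30.4) = 21%, against 1 − exp(−2 × 28/30.4) = 84%
- Part 2A (56 days): 37% against 97%, by the same formula

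**The case against.** The strongest reply is that little is lost in practice. Every TEAE is listed with its duration and the parts in which it started and stopped, and with 4 subjects that listing is more informative than any table. The analysis is descriptive (Protocol 12.2), so the primary label drives no test. Protocol 12.2.3.1 does not require event counts. SAP 1 places table specifications in a separate document that is not available here, and sorting by total events fits with an event column there. Protocol 12.2 also promises that the final report will discuss deviations.

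Most of this stands, and it limits the size of the point. It does not remove it. An open tabulation unit in 12.2.3.1 does not authorise replacing the endpoint stated in 12.2.2.1. A column that may exist in table shells is not specified in the plan. A listing without a counting rule does not fix the total, and a departure is discussed in the report only if someone recognises it.

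A reader might infer more: that the subject-level measure saturates near 100% over a year and so cannot separate a well-tolerated drug from a poorly tolerated one. The documents do not support that. They give no event rate, the effect applies only to the whole-study any-TEAE row, and rows by term and by part need not saturate (steps 4 and 5). The 394 days also assume that every subject completes Part 2B, while treatment can end at Day 28 or Day 84. Nor does SAP 7.1 say that every table counts a subject once per preferred term; that sentence is tied to the summary by relationship.

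**Conclusion.** The point holds on the text. The SAP removes the protocol's primary safety endpoint from its primary list, rewords it, specifies summaries in subjects with no severity table, and does not declare the change in SAP 15. This conclusion needs no assumed rate. It concerns what the SAP specifies, not what unseen table shells may contain.

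The impact is low: 4 subjects, no inference, complete listings. Any remark about saturation should be confined to the whole-study any-TEAE row and marked as conditional. Under a constant rate and full follow-up, that row is about 66% at 1 event per subject-year and reaches 95% only at about 2.8 or more.

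**What to change.** - **SAP 2.3:** restore the number and severity of TEAEs as the primary safety endpoint.
- **SAP 7.1, counts:** add the number of events beside n (%) of subjects in the overall, SOC/preferred-term and related-TEAE tables, for the whole study and by part.
- **SAP 7.1, severity:** add a table by maximum severity, which also gives the imputation rule in 13.5.5 a use.
- **SAP 7.1, counting rule:** state that a continuing or regraded event counts as one event in the whole-study total. Footnote that an event that worsens in a later part appears in both parts, so part totals may sum to more than the whole-study total.
- **SAP 15:** record any departure from the protocol that remains.

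The cost is one column in tables already planned, one short table and a few sentences. The sort order already requires an event count. The extra work is linking regraded records to their episode, which is small with 4 subjects.

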## 7.2 Clinical Laboratory Data

Observed and change from baseline values will be summarized for all hematology, chemistry and coagulation clinical laboratory parameters using descriptive statistics, by part of the study and study visit.

All laboratory data will be listed. The listing will include changes from baseline values and values that are outside the reference range will be flagged.

## 7.3 Vital Signs

Observed and change from baseline values will be listed. In the listing, values of potential clinical significance will be flagged. These are defined in the table below.

Vital Sign Parameter	Flag	Criteria
		Observed Value
Systolic blood pressure (mmHg)	High	$\geq 165$
	Low	$\leq 80$
Diastolic blood pressure (mmHg)	High	$\geq 95$
	Low	$\leq 40$
Pulse rate (beats per minute)	High	$\geq 120$
	Low	$\leq 40$
Temperature (°C)	High	$\geq 38$
	Low	-

## 7.4 Electrocardiogram (ECG)

Observed and change from baseline values will be listed. In the listing, values of potential clinical significance will be flagged. These are defined in the table below.

Table 2: Criteria for Potentially Clinically Significant ECG Values			
Vital Sign Parameter	Flag	Criteria	
		Observed Value	Change from baseline
QT, QTcB, QTcF (msec)	High	≥450	≥30
	Low	-	-
PR (msec)	High	≥240	-
	Low	≤100	-
QRS (msec)	High	≥140	-
	Low	-	-
Heart rate (bpm)	High	≥120	-
	Low	≤40	-

## 7.5 Other Safety Data

Immunogenicity and physical examination data will be listed.

## 8. PHARMACOKINETIC ANALYSIS

All PK analyses will be based on the PK Set.

### 8.1 Handling BLQ Values

APL-2 concentrations reported as below the limit of quantification (BLQ) will be taken as zero for linear plots, and equal to the lower limit of quantification (LLOQ) for semi-logarithmic plots.

If a BLQ value falls between two quantifiable concentrations the value will be set equal to the LLOQ, unless it's exclusion can be justified (e.g. implausibility given the profile observed and known PK properties).

### 8.2 Drug Concentration

Linear and log-linear individual concentration profile plots against time will be produced with each subject being identifiable. A dotted line will be used to identify follow-up (Part 3). The actual sampling day will be used on the x-axis.

A listing of all concentration data will be presented. The actual time and deviation from nominal time will also be listed.

### **8.3 Pharmacokinetic Parameters**

PK parameters will be listed.

## **9. PHARMACODYNAMIC ANALYSIS**

All PD analyses will be based on the PD Set.

### **9.1 Handling BLQ Values**

If a baseline PD value is zero, then the percentage changes from baseline will not be calculated. If a PD value is BLQ then the value will be set to the LLOQ. Similarly, for the PD plots, a BLQ value will be set equal to LLOQ.

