4.1.1 Paroxysmal Nocturnal Hemoglobinuria

PNH is an acquired, clonal, non-malignant hematological disease characterized by complement-mediated RBC hemolysis with or without hemoglobinuria, an increased susceptibility to thrombotic episodes, and/or some degree of bone marrow dysfunction. The onset of PNH is often insidious. Although there have been reports of spontaneous remission, the course of the disease is generally chronic and progressive.

It has been known for many years that PNH is caused by complement-mediated lysis of erythrocyte clones lacking functional CD55 and CD59 on their surface to protect them against this process. As such, these erythrocytes are particularly susceptible to the membrane attack complex (MAC) and have been shown to lyse readily in the presence of complement activation.

Any therapy that effectively inhibits MAC formation is anticipated to be a plausible candidate-treatment for PNH. Indeed, eculizumab is a monoclonal anti-C5 antibody that inhibits the formation of the MAC, and eculizumab treatment has been approved for the treatment of this serious condition. However, inhibition of MAC formation does not appear to be sufficient to fully control the disease, as many PNH patients receiving eculizumab treatment still suffer from anemia, with only roughly 13% of patients being classified as complete responders, i.e. achieving transfusion independence and normal Hb levels. Most of the patients (53%) were classified as partial responders with decreased transfusion needs and reduced LD, and 33% of patients were poor responders, with unchanged transfusion needs and persistent symptoms ([DeZern, 2013](#)).

Recent studies have suggested that significant opsonization of PNH erythrocytes by C3 fragments is observed in patients receiving eculizumab treatment. This opsonization is believed to cause the removal of erythrocytes by the spleen and the liver, resulting in extravascular hemolysis. Extravascular hemolysis can be significant in a subset of eculizumab-treated PNH patients and is considered to be the principal contributor to the lack of complete eculizumab response in most patients. It is reasonable, therefore, to expect that a treatment able to inhibit both MAC formation and C3 opsonization will provide improved therapeutic benefit to PNH patients compared to eculizumab.

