### 2.3.5 Pharmacodynamics Endpoints

- Changes from baseline and percentage changes from baseline in complement C3 levels
- Changes from baseline and percentage of baseline in complement CH50 and AP50 levels
- Changes from baseline and percentage changes from baseline in C3 deposition on RBC cells
- Changes from baseline and percentage changes from baseline in Clonal distribution of PNH RBCs

In addition the following endpoints will be derived:

- Clonal distribution of PNH RBCs (percent Type II + III); this is simply the sum of the clonal distribution of PNH RBCs Type II and Type III.
- C3d deposition on RBC cells (percent Type II + III); this is the number of events for C3d deposition on RBC cells (Type II) plus number of events for C3d deposition on RBC cells (Type III) divided by number of events for PNH CD59 Type II and III expressed as a percent.

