### **9.2 Pharmacodynamic Data**

Absolute PD parameter values will be listed together with changes from baseline and percentage changes from baseline (for CH50 and AP50 percentage of baseline will be listed instead), by study part and study visit.

Absolute values, changes from baseline and percentage changes from baseline will be plotted for the complement parameter C3 by study day with each subject being identifiable. A dotted line will be used to identify follow-up (Part 3). The actual sampling day will be used on the x-axis. The changes and percentage changes from baseline plots will include a reference line for 0 on the y-axis.

For the complement parameters CH50 and AP50 only percentage of baseline values will be plotted by study day with each subject being identifiable. A dotted line will be used to identify follow-up (Part 3). The actual sampling day will be used on the x-axis. A reference line for 100 will be presented on the y-axis.

For the complement parameter C3 values throughout the study will be plotted against time for each subject individually (i.e. one plot per subject). On study transfusions (PRBC only) will be identified on the plot as a vertical line at the relevant study day. Above the profile plot a separate plot will be displayed which shows the APL-2 dose by study day. The study day on both plots will be aligned. For the complement parameters CH50 and AP50 the same plot will be generated using percentage of baseline values instead.

Absolute values in PNH granulocytes (percent FLAER) will be plotted by study day with each subject being identifiable. A dotted line will be used to identify follow-up (Part 3). The actual sampling day will be used on the x-axis. These plots will be repeated for PNH monocytes (percent FLAER).

Individual subject plots of the percentage distribution will be presented for the C3 deposition on RBC cells parameters, with all parameters included on the same subject plot. A dotted line will be used to identify follow-up (Part 3). The actual sampling day will be used on the x-axis. The plot will identify on study transfusions (PRBC only) as a vertical line at the relevant study day; and above the profile plot a separate plot will be displayed which shows the APL-2 dose by study day. The study day on both plots will be aligned. These plots will be repeated for clonal distribution of PNH RBCs parameters.

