### **13.2 Definition of Baseline**

Baseline is defined as the last observed value prior to taking the first dose of investigational product (based on dates or date/times).

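### SAP 9.1 withholds percentage change for a zero PD baseline but not for a BLQ one, so the assay limit becomes the denominator

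*SAP*

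**What the plan says.** SAP 9.1 consists of three rules for PD data. The first is a safeguard: "If a baseline PD value is zero, then the percentage changes from baseline will not be calculated". The second is a substitution: "If a PD value is BLQ then the value will be set to the LLOQ". The third repeats the substitution for figures: "Similarly, for the PD plots, a BLQ value will be set equal to LLOQ".

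SAP 13.2 adds no special case for baseline: "Baseline is defined as the last observed value prior to taking the first dose of investigational product".

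The quantities affected are set out in SAP 2.3.5 and 9.2. Change and percentage change are required for C3, for clonal distribution of PNH red cells and for C3 deposition ("Changes from baseline and percentage changes from baseline in C3 deposition on RBC cells"). CH50 and AP50 are handled differently: "for CH50 and AP50 percentage of baseline will be listed instead", and in the figures "For the complement parameters CH50 and AP50 only percentage of baseline values will be plotted by study day with each subject being identifiable". The CH50 and AP50 plots that overlay all subjects carry a reference line at 100. The single-subject plots have the APL-2 dose drawn above them on the same time axis.

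For drug concentrations the SAP uses a different convention. Section 8.1 sets BLQ to zero on linear plots and to the LLOQ on semi-logarithmic ones. The protocol (12.2.7) has a BLQ rule for concentrations only.

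**The concern.** The safeguard shows that the authors saw the problem of a percentage with nothing in the denominator. It covers only a baseline recorded as zero. A baseline reported as BLQ is replaced by the LLOQ, which is above zero, so the percentage is calculated. Its denominator is then a property of the assay, not of the subject.

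There are two related gaps. The safeguard names percentage change but not percentage of baseline, the quantity used for CH50 and AP50. And a post-dose BLQ result enters the figures at the LLOQ with no instruction in SAP 9.1 or 9.2 to show that it is a limit and not a reading. For CH50 and AP50 no absolute-value plot is planned that would let the reader see this.

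What is at stake is how individual PD profiles are read. SAP 9.2 plans no PD summary tables, so the listings and plots are the whole PD result. A meaningless percentage would stand there as a data point.

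**Working it through.** The documents state no LLOQ and no baseline PD value, so there is no figure to reproduce. The results below follow from the rules by algebra; every ratio put in is an assumption.

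**1. BLQ baseline, quantifiable visit value.** Let L be the LLOQ and x = kL the visit value. Under SAP 9.1:

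- percentage change = 100 × (kL − L)/L = 100 × (k − 1)
- percentage of baseline = 100 × kL/L = 100 × k

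If the true baseline is fL, with f between 0 and 1, the true percentage change is 100 × (k − f)/f.

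| Visit value | SAP rule | True baseline 0.5 L | True baseline 0.1 L |
|---|---|---|---|
| 1 L | 0% | 100% | 900% |
| 2 L | 100% | 300% | 1900% |
| 5 L | 400% | 900% | 4900% |
| 10 L | 900% | 1900% | 9900% |

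The reported figure is the same whatever the true baseline, and the gap has no bound as f approaches zero.

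**2. Same visit value, different assay limits.** Take a visit value of 5 (any unit) and a BLQ baseline:

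- L = 1: (5 − 1)/1 = +400%, absolute change 4.0
- L = 0.5: (5 − 0.5)/0.5 = +900%, absolute change 4.5
- L = 0.1: (5 − 0.1)/0.1 = +4900%, absolute change 4.9

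The absolute change moves little. With true baseline b between 0 and L, the true change x − b differs from x − L by at most L. Absolute change is therefore still usable with a BLQ baseline, and percentage change is not.

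**3. BLQ at both baseline and visit.** Percentage change = 100 × (L − L)/L = 0%; percentage of baseline = 100 × L/L = 100%. For CH50 and AP50 the point falls on the reference line at 100, although the data do not show whether activity rose, fell or stayed the same.

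**4. Quantifiable baseline, BLQ after dosing.** Percentage of baseline = 100 × L/baseline. If L is 1%, 5%, 10%, 20%, 30% or 50% of the subject's baseline, the plotted value is 1, 5, 10, 20, 30 or 50. With an assumed L of 10 units, baselines of 150, 100 and 40 give 10/150 = 6.7%, 10/100 = 10% and 10/40 = 25%. The true value is at or below the plotted one in every case, so this is an upper bound. Subjects who are all simply BLQ plot at different heights because their baselines differ.

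**5. Zero baseline for CH50 or AP50.** Percentage of baseline = 100 × x/0 is undefined. The safeguard in SAP 9.1 does not name this quantity.

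**The case against.** Several points against giving this much weight are sound.

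- **Direction.** Setting a post-dose BLQ result to the LLOQ understates a fall in complement activity. It does not flatter the drug, and it is a reasonable plotting convention to keep.
- **Context on the page.** Percentage change is plotted only for C3, whose absolute values are plotted too. Elsewhere it is only listed, beside the value and the absolute change.
- **Marking.** SAP section 1 puts specifications for tables, figures and listings in a separate document, which may provide a BLQ symbol. SAP 13.1 requires all data to be listed. So it can be said that SAP 9.1 and 9.2 do not require a mark, but not that the points will be unmarked.
- **Likelihood for CH50 and AP50.** A BLQ baseline needs an untreated subject with unquantifiable complement activity. Hereditary complement deficiency and prior eculizumab are both exclusions (protocol 7.2).

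Two stronger readings are tempting, and the documents do not support them. A reader might infer that fully suppressed AP50 or CH50 will be shown as residual activity. BLQ does not establish full suppression, though. Protocol 4.1.5 reports a dose-dependent reduction in AP50, not abolition, and protocol 4.2.2 describes a dose chosen to leave some complement activity.

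A reader might also infer that C3 deposition will often be BLQ at baseline, because these subjects have never had eculizumab and the protocol says that "significant opsonization of PNH erythrocytes by C3 fragments is observed in patients receiving eculizumab treatment". That sentence does not describe untreated patients, and a low value need not be BLQ. The derived C3d endpoint in SAP 2.3.5 is a ratio of event counts, which can be exactly zero and is then already covered. No LLOQ is given for this readout.

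None of this closes the gap for a baseline that is BLQ. The substitution is a stated rule and applies to baseline as written.

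**Conclusion.** The point holds as a gap in a stated rule. If a PD baseline is BLQ, SAP 9.1 produces a percentage whose denominator is the assay limit, and a BLQ pair reads as 0% change or 100% of baseline. The safeguard also omits percentage of baseline. Post-dose substitution is conservative and needs only to be identified as censored.

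The priority is low. PD is an exploratory objective, enrolment closed at four subjects, the protocol plans no formal inference (12.2), and no PD mean or test depends on the rule. The algebra rests only on SAP 9.1, 9.2 and 13.2. The percentages above are illustrations and not predicted effects in this trial, because the documents give neither the LLOQs nor the frequency of BLQ results.

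**What to change.** Amend SAP 9.1, which SAP section 1 allows before database lock:

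1. If the baseline PD value is zero or BLQ, calculate neither percentage change nor percentage of baseline. List the value and the absolute change, flagged as BLQ where that applies.
2. Keep the LLOQ for post-dose BLQ values, but mark these points as censored in the plots (for example with an open symbol) and list the derived percentage as an upper bound (≤).
3. State the LLOQ of each PD assay that has one.

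The cost is a few sentences and a plot symbol. The real downside is that a subject with a BLQ CH50 or AP50 baseline loses the whole percentage-of-baseline curve, one of at most four. That subject's absolute values should be plotted instead.
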